Arm B (Cohort B) is a surgical arm (N=16) that will allow for evaluation of the effects on the tumor immune microenvironment of INCMGA00012, INCAGN01876, and SRS. In order to be enrolled on this arm, subjects must have a clinical indication for surgical resection of the recurrent GBM tumor. Prior to planned surgical resection, subjects receive neoadjuvant immunotherapy (one of two possible combinations, as outlined below). Subjects then undergo surgery. Postoperatively, the immunotherapy combination of INCMGA00012 (IV every 4 weeks) and INCAGN01876 (IV every 2 weeks) is resumed and continued until disease progression, unacceptable toxicity, or for 2 years, whichever occurs first. Subjects in the surgical arm with a focus of contrast-enhancing tumor that is amenable to SRS will be assigned to surgical sub-arm #1 of Cohort B (N=8). These subjects will receive neoadjuvant INCMGA00012 + INCAGN01876 + SRS. All other subjects enrolled on Cohort B (N=8) are treated with neoadjuvant INCMGA00012 + INCAGN01876 (without SRS).

Schema:

Objectives:

Primary Objective:

- To determine the efficacy of the combination of INCMGA00012, INCAGN01876, and SRS in recurrent GBM, as measured by the overall objective response rate (ORR)

Secondary Objectives:

- To evaluate the safety and tolerability of the combination of INCMGA00012, INCAGN01876, and SRS in recurrent GBM
- To determine the progression-free survival (PFS) and overall survival (OS) of patients with recurrent GBM treated with the combination of INCMGA00012, INCAGN01876, and SRS

Exploratory Objectives:

- To evaluate the biologic effect of the combination of INCMGA00012 and INCAGN01876 on the GBM tumor immunemicroenvironment
- To evaluate the biologic effect of the combination of INCMGA00012 and INCAGN01876, with or without SRS, on the GBM tumor immune microenvironment
- To evaluate the pharmacodynamic impact of the combination of INCMGA00012, INCAGN01876, and SRS on peripheral blood immune cell populations
- To evaluate the pharmacokinetics (PK) of INCAGN01876 in patients with glioblastoma
- To determine whether anti-drug antibodies (ADA) form against INCAGN01876 in patients with glioblastoma
- To detect tumor and/or blood biomarkers associated with the outcomes of OS, PFS, and/or ORR in patients with recurrent GBM treated with the combination of INCMGA00012, INCAGN01876, and SRS

Endpoints:

Primary Endpoint:

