4. INCLUSION AND EXCLUSION CRITERIA

4.1 Inclusion Criteria

Subjects must meet all of the following criteria:

1. Prior histopathologically proven diagnosis of World Health Organization (WHO) grade IV glioblastoma, OR histopathologically proven diagnosis of gliosarcoma, OR molecular diagnosis of glioblastoma per c-IMPACT-NOW criteria (“diffuse astrocytic glioma, IDH-wildtype, with molecular features of glioblastoma, WHO grade IV”; this requires presence of either amplification of *EGFR*, whole chromosome 7 gain AND whole chromosome 10 loss, or *TERT*

promoter mutation). Participants are eligible if the prior diagnosis was low-grade glioma and a subsequent histological diagnosis of glioblastoma was made (e.g. secondary GBM).

2. Participants must have glial tumor that is recurrent following prior first-line radiation therapy (prior dose must have been 40-75 Gy and may have been either photon or proton radiation), and must have unequivocal evidence of tumor progression by MRI scan

3. Cohort A and Sub-Arm 1 of Cohort B only: Patient must have at least one measurable (≥ 1 cm x 1 cm) contrast-enhancing tumor focus for which stereotactic radiosurgery (SRS) is clinically indicated, as determined by the Investigator, and must be able to achieve radiation target coverage without exceeding dose constraints. The contrast-enhancing target must not be larger than 4 cm in maximal diameter. Multifocal disease is allowed as long as this criterion is met

- Sub-Arms 2 of Cohort B can have any size tumor, and the tumor does not need to be amenable to SRS

4. Cohort B (surgical) patients only: patients must be undergoing surgery that is clinically indicated as determined by their care providers

5. Tumor O-6-methylguanine-deoxyribonucleic acid (DNA) methyltransferase (MGMT) methylation status must be available from any prior GBM tumor specimen; results of routinely used methods for MGMT methylation testing (e.g. mutagenically separated polymerase chain reaction [MSPCR] or quantitative polymerase chain reaction [PCR]) are acceptable)

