6. Patients may have had treatment for an unlimited number of prior relapses but must not have had prior bevacizumab or other vascular endothelial growth factor (VEGF/VEGFR) inhibitors (exception: prior bevacizumab is allowed if it was administered for the treatment of radiation necrosis rather than progressive tumor and was stopped at least 4 weeks prior to MRI showing demonstrating tumor progression). Prior gliadel wafers are only allowed if placed during the first surgery for GBM at initial diagnosis.

7. Patients must have recovered from severe toxicity of prior therapy; the following intervals from previous treatments are required to be eligible:

- 12 weeks from completion of radiation
- 6 weeks from a nitrosourea cytotoxic chemotherapy
- 3 weeks from a non-nitrosourea cytotoxic chemotherapy
- 4 weeks from any investigational (not Food and Drug Administration [FDA]-approved for glioblastoma) agents, or within a time interval less than at least 5 half-lives of the investigational agent whichever is shorter
- 3 weeks from any major surgery, including brain surgery for recurrent tumor resection

8. If patient is on systemic corticosteroids to treat brain edema and/or brain edema-related symptoms, the dose must be 2mg of dexamethasone (or equivalent) daily or less for a minimum of 5 days prior to first dose of study drug.

9. Patients must be able to swallow oral medications

10. Age 18 or older

11. Karnofsky performance status ≥ 60
12. Life expectancy >3 months
13. Absolute lymphocyte count $\geq 500/uL$
14. Adequate hepatic function within 7 days prior to start of study treatment, defined as follows
 - Total bilirubin (except patients with Gilbert's Syndrome, who are eligible for the study but exempt from the total bilirubin eligibility criterion) ≤ 2.0 mg/dl
 - ALT and AST $\leq 2.5x$ upper limit of normal (ULN)
15. Adequate renal function within 7 days prior to start of study treatment, defined as follows:
 - Serum creatinine ≤ 1.5 x institutional ULN OR calculated creatinine clearance (glomerular filtration rate can also be used in place of creatinine or CrCl) ≥ 50 mL/min for subjects with creatinine levels $>1.5x$ institutional ULN
16. Reproductive Status
 - a) Women of childbearing potential (WOCBP) must have a negative serum or urine pregnancy test (minimum sensitivity 25 IU/L or equivalent units of HCG) within 7 days prior to the start of study drug.

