7.9 Tissue/Blood collection for correlative analyses, PK, and ADA

For all subjects in this study (both Cohort A and Cohort B), informed consent will be obtained to collect a formalin-fixed, paraffin-embedded (FFPE) preserved component of tumor tissue from the subject's initial surgical tumor resection for exploratory correlative analyses. This surgery

will have already been performed prior to their enrollment on this protocol as part of standard of care therapy for glioblastoma.

For subject in the surgical arm only (Cohort B, N=16), both fresh frozen and FFPE preserved components of tumor tissue will also be collected from the surgery that subjects will undergo as part of this protocol (i.e., the subject's surgery for recurrent GBM).

In addition, in both Cohorts A and B 60 mL of peripheral blood will also be collected for future exploratory correlative analyses. These 60 mL blood samples will be collected at the time points outlined in the SOE (**Table 8** and **Table 9**).

All subjects will be asked to consent to collection of an FFPE preserved component of tumor tissue from any surgical brain tumor resection or brain tumor biopsy that is performed (as clinically indicated) after the subject has discontinued the study treatment. If a subject comes off study for progressive disease, initiates another treatment regimen per standard of care, and then has another tumor resection, collection of FFPE preserved tissue will not occur.

The exploratory endpoints of this study are outlined in [Section 2](#). All correlative analyses will be performed in University of Pennsylvania laboratories with the following exceptions: pharmacokinetic (PK) and anti-drug antibody (ADA) measurements will be performed by Syneos Health, and GITR expression by IHC will be performed by Mosaic Laboratories. In addition to the correlative assays listed in [Section 2](#), other assays relevant to understanding mechanisms or predictors of clinical benefit and/or resistance to INCMGA00012 and INCAGN01876 in GBM may be performed on these tissue and blood samples in the future based upon emerging data and future hypotheses. The informed consent form reflects this flexibility for future research use of subject biospecimens collected during the course of this study.

No results of tissue or blood correlatives will be recorded in the subject's electronic medical record and will not be used in any way to guide treatment or clinical decision making.

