For analysis of correlative data, variable distributions will be presented graphically and descriptively at each time point; if needed, appropriate transformations will be performed. Paired t-tests will be used to assess change from pre- to post-treatment for exploratory endpoints that are normally distributed. Wilcoxon signed-rank tests will be used to assess change from pre- to post-treatment for exploratory endpoints that are not normally distributed. Multiple comparison adjustment using false discovery rate (FDR) will be used. The sample size of 16 subjects in the surgical arm of the study (Cohort B), with N=8 per sub-arm provides 85% power with one-sided alpha of 0.05 to detect the difference between the null hypothesis of a CD8+ tumor-infiltrating lymphocyte score of 1 and the alternative hypothesis of a CD8+ tumor-infiltrating lymphocyte score of 1.85. These numbers are based on the pre- and post- CD8+ tumor-infiltrating lymphocyte scoring system (scored 0 to 3, least to most CD8+ T cell infiltration) used in our prior CAR T cell trial in recurrent GBM (O'Rourke, *Sci Transl Med* 2017), which is one of the few immunotherapies shown to increase tumor T cell infiltration in this disease. In that study,

pre-CAR T cell GBM specimens had a mean score of 1 (standard deviation 0.1) and post-CAR T cell GBM specimens had a mean score of 1.85 (standard deviation 0.80).

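### The only pre-study tumour tissue collected comes from the initial resection, so a paired tumour change in Cohort B cannot be attributed to the study regimen alone

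*Combined protocol and SAP*

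**What the plan says.** Section 7.9 has one source of tumour tissue from before enrolment: archival FFPE material from the "initial surgical tumor resection for exploratory correlative analyses". That operation "will have already been performed prior to their enrollment on this protocol as part of standard of care therapy for glioblastoma". In Cohort B, "both fresh frozen and FFPE preserved components of tumor tissue will also be collected from the surgery that subjects will undergo as" part of the study. The synopsis places study treatment ahead of that operation: "Prior to planned surgical resection, subjects receive neoadjuvant immunotherapy". Sub-arm 1 also receives SRS first. Table 9 lists tumour tissue only at the surgery. The remaining collection in 7.9 is from operations or biopsies after study treatment has stopped.

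Section 8.2.2 states: "Paired t-tests will be used to assess change from pre- to post-treatment for exploratory endpoints" where the data are normal. Signed-rank tests are used otherwise, with FDR adjustment. It does not say which tumour specimen is 'pre'. The same section claims 85% power at one-sided 0.05, with eight subjects per sub-arm, for a CD8+ score of 1 under the null against 1.85. The values come from an earlier CAR T-cell trial (pre: mean 1, SD 0.1; post: mean 1.85, SD 0.80).

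Section 4.1 determines who is paired. Inclusion 2 requires recurrence after first-line radiation, and Inclusion 7 requires 12 weeks since it ended. Inclusion 6 adds: "Patients may have had treatment for an unlimited number of prior relapses". Inclusion 7 permits entry "3 weeks from any major surgery, including brain surgery for recurrent tumor resection". Inclusion 1 adds: "Participants are eligible if the prior diagnosis was low-grade glioma and a subsequent histological diagnosis of glioblastoma was made".

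**The concern.** Cohort B exists to show what the regimen does to the tumour immune microenvironment, and half of the planned 32 subjects are enrolled for it. A paired test has that meaning only if study treatment is the main thing that happened between the two specimens. Here the earlier specimen predates the subject's whole course of prior therapy and the recurrence itself. A change in infiltration could come from any of these, in either direction, and the test cannot separate them. FDR adjustment deals with multiplicity and does nothing about a systematic shift.

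Later pre-study tissue is foreseeable. The criteria allow recurrent resection shortly before entry, and Inclusion 5 accepts an MGMT result from any earlier GBM specimen. Section 7.9 does not ask for such tissue for the correlatives.

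**Working it through.** **1. Which specimen can be 'pre'.**

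| Tumour tissue (Section 7.9, Table 9) | Taken | Possible role |
|---|---|---|
| Initial resection, FFPE | Before enrolment | 'Pre': the only candidate |
| Cohort B surgery, frozen and FFPE | After neoadjuvant treatment | 'Post' |
| Later resection or biopsy, FFPE | After study treatment stops | Not a baseline |

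That the initial resection is 'pre' is therefore reached by elimination. Section 8.2.2 does not say so.

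**2. What lies between the two specimens.** Section 1.2 describes first-line care as resection, then radiotherapy, often with temozolomide. On that sequence, each of the 16 planned pairs spans radiation, at least 12 further weeks, and recurrence, before any study treatment. Some will also span treatment for further relapses; the documents give no frequencies. Write the expected paired change as δ + b, where δ is the effect of the study regimen and b is everything else. The paired test estimates only the sum. The plan has no untreated recurrent comparison, no adjustment for interval or intervening therapy, and no statement limiting attribution.

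**3. The plan's own figure.** Power = 1 − F(t₀.₉₅,ₙ₋₁; n−1, λ), where F is the noncentral t distribution and λ = difference × √n / SD.

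- One-sample t, n=8, difference 0.85, SD 0.80: λ = 0.85 × √8 / 0.80 = 3.005, power **85.4%**.
- Paired t, with SD of change = √(0.1² + 0.8² − 2ρ × 0.1 × 0.8). At ρ=0 the SD is 0.806 and power is **84.9%**. At ρ=−0.5 power is 81.2%, and at ρ=0.5 it is 88.7%.

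The stated 85% is reproduced. A one-sample test against 1 and a paired test with ρ=0 both round to it, so the figure does not show which test, or which baseline, was intended.

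**4. Consequence of a non-study shift.** The documents give no value for b, so this is an illustration over an assumed range, with SD of change 0.80 and one-sided 5%. With δ=0, the chance of a significant increase is:

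| Assumed b (score points) | n=8 | n=16 |
|---|---|---|
| 0 | 5.0% | 5.0% |
| 0.1 | 9.3% | 12.2% |
| 0.2 | 15.8% | 24.5% |
| 0.25 | 19.9% | 32.6% |
| 0.4 | 35.7% | 60.4% |
| 0.5 | 48.0% | 77.0% |

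Pooling the sub-arms makes this worse, because more data estimate the same biased quantity more precisely. In the other direction, with a true δ of 0.85 and n=8, power falls to 66.4% (b=−0.2), 41.7% (b=−0.4) or 29.9% (b=−0.5).

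**5. Weight of one mismatched baseline.** If one of eight baselines is off by one score point, the mean change moves by 1/8 = 0.125. That is 0.125 / 0.85 = 15% of the target difference.

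**The case against.** Several counter-arguments are fair.

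- **The archival pairing is inferred.** The paired-test sentence covers all exploratory endpoints, including blood, which has a Day 1 sample on study. The comparison of treatment with and without SRS can use post-treatment tissue. The CD8+ power figure fits a test against a fixed score of 1. All of this stands and limits the point to paired tumour comparisons. It does not answer it, because any such comparison has only the initial resection to draw on.
- **The endpoints are exploratory, and no passage says a change would be reported as a drug effect.** True, which is why this is an improvement rather than a defect in the trial's main conclusion.
- **One uniform landmark specimen is defensible.** Taking the most recent specimen mixes newly diagnosed and recurrent baselines within eight pairs. This stands as a cost, and it is the reason for a sensitivity analysis.
- **The remedy is partial.** Section 1.2 says repeat surgery is indicated in only a minority of relapsed patients, so many subjects may have only the first specimen. This also stands.

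Three stronger readings are tempting but unsupported. A reader might infer that every secondary-GBM subject contributes a low-grade 'pre' sample. However, 7.9 describes the operation as standard care for glioblastoma, which may mean the first GBM surgery, so the text is ambiguous. For the same subjects, a rule excluding pairs with only low-grade tissue may look necessary. Inclusion 1 already requires a later histological GBM diagnosis, so such a rule would have almost nothing to act on. Finally, dividing a one-point baseline error by the pre-treatment SD of 0.1 gives 10 SDs. The test runs on the SD of change, about 0.80, where that error is 1.25 SDs in one pair and has the modest effect shown in step 5.

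**Conclusion.** The point holds as a cheap improvement. As written, any paired pre/post tumour result in Cohort B combines the study regimen with prior radiation, often temozolomide, and recurrence, and the plan neither names the baseline specimen nor states this limit. The conclusion rests on two things: by elimination, the initial resection is the only possible 'pre' tissue, and first-line treatment followed the sequence in Section 1.2.

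The size is not known from the documents. The 20% to 48% rejection rate at n=8 depends wholly on the assumed shift of 0.25 to 0.5 points and an SD of change of 0.80. The 85% power arithmetic itself is sound. For secondary GBM there is a separate wording ambiguity about which operation is the initial one. The blood correlatives, the sub-arm comparison of post-treatment tissue and the Cohort A ORR analysis are not affected.

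**What to change.** **Section 7.9:** in addition to the initial specimen, collect archival FFPE tissue from the most recent pre-enrolment resection or biopsy showing glioblastoma, where available. Say whether 'initial' means the first glioma surgery or the first GBM surgery.

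**Section 8.2.2:**

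- Name the most recent pre-enrolment GBM specimen as the 'pre' sample for paired tumour tests.
- Record, for each pair, the interval and the treatments between specimens.
- Add a sensitivity analysis using the initial specimen.
- State that the paired change reflects recurrence and prior therapy as well as the study regimen.

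Fixing this before analysis also prevents a choice of baseline after results are seen.

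**Cost:** a few sentences in the two sections, retrieval of one more archival block for some subjects, and no new patient procedure. The price is baselines from mixed disease stages. The confounding is reduced where a later specimen exists and is unchanged for subjects with only the initial one, so the interpretation statement is needed in every case.

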7.10 Protocol exceptions (prospective action)

An ***exception*** is defined as a one-time, intentional action or process that departs from the approved study protocol, intended for one occurrence. If the action disrupts the study progress, such that the study design or outcomes may be compromised, or the action compromises the safety and/or welfare of study subjects, advance documented approval from the Regulatory Sponsor and local regulatory review committees, per institutional guidelines, is required. Approval from the Regulatory Sponsor must be received prior to submission to the local regulatory review committees.

7.11 Protocol Deviations (retrospective action)

A ***deviation*** is defined as a one-time, unintentional action or process that departs from the approved study protocol, involving one incident and identified retrospectively. If the deviation disrupts study progress, such that the study design or outcomes may be compromised, or the deviation compromises the safety and/or welfare of study subjects, the deviation must be reported to the Regulatory Sponsor within 24 hours of PI knowledge and to local regulatory review committees per institutional guidelines.

Report the following information on the Sponsor's exception/deviation form:

- Protocol number
- Subject number
- Description of the exception or deviation
- Impact on subject safety
- Impact on data integrity

Deviations that are assessed by the PI to not disrupt the study progress, such as not affecting the study design or outcome, or compromising the safety and/or welfare of study subjects, should be documented in site records and contain documentation of the PI's assessment.

8 STATISTICAL PLAN

8.1 Definition of Primary Endpoint

The primary efficacy endpoint of this study is objective radiographic response (ORR), as defined by modified Response Assessment in Neuro-Oncology (mRANO) criteria ([Ellingson et al, Neurotherapeutics 2017](#)). Per mRANO criteria, ORR is defined as the presence or absence of an objective radiographic tumor response, either a) partial or complete response; OR b) absence of partial or complete response, i.e., a binary endpoint. A two-sided 95% confidence interval for ORR will be calculated.

Only subjects enrolled on Cohort A who have (1) not been replaced AND (2) received SRS and at least one dose of both study drugs are evaluable for the primary endpoint.

8.2 Statistical Methods

8.2.1 Primary Endpoint Analysis (Efficacy of Regimen)

The primary efficacy hypothesis of this study is that the proportion of subjects who experience an objective radiographic response will be 25% or higher. We will test this hypothesis against the null hypothesis of 5% of subjects experiencing an objective response using an exact single-stage phase II design for the primary study cohort (Cohort A; Non-surgical). A sample size of 16 evaluable subjects is required for 80% power. A one-sided significance level has been set at 0.05. A subject is considered evaluable for the primary endpoint if (a) the subject is one of the 16 subjects enrolled onto Cohort A at the same dose and schedule of study drugs that is determined to be the final dose/schedule based on the safety run-in phase, AND (b) the subject has received at least one dose of BOTH study drugs AND has received at least one fraction of SRS.

In one of the largest series of patients with recurrent high-grade glioma treated with hypofractionated stereotactic radiation therapy alone, ~10% of patients experienced a minimal response of the irradiated tumor by MacDonald Criteria; no patients experienced a partial response ([Fogh, J Clin Oncol 2010](#)). For patients who have one tumor site irradiated while other sites of tumor are not irradiated, such as some of the subjects who will be enrolled in the current protocol, no responses would be expected in non-irradiated tumor. With these data in mind,

coupled with the historic overall response rate of ~10% to single-agent lomustine (a standard of care) in recurrent GBM (Batchelor TT, et al. *J Clin Oncol* 2013), we have designated ORR=5% as the null hypothesis.

The alternative hypothesis, a 25% ORR, would be a clinically significant difference that would suggest this regimen is worthy of further investigation.

